APPENDIX A: STUDY PROCEDURES

APPENDIX A.1: Planned laboratory tests

Hematology – Hemoglobin, WBC and differential count, platelet count. **Biochemistry** – BUN, creatinine, total bilirubin, AST, ALT.

Blood samples have a target volume of 3ml, a minimum of 1.5 ml.

Immunology – HIV rapid test done as part of screening

Probiotic carriage- PCR is done on stool samples to detect *L. reuteri* per laboratory SOP.

Appendix B. Definitions for Adverse Events Monitoring

Safety of *Lactobacillus reuteri* in healthy children ages 2-24 months in Peru

Estimating Clinical Severity:

Grade 1 (mild): Symptoms causing no or minimal interference with usual activities

Grade 2 (moderate): Symptoms causing greater than minimal interference with usual activities

Grade 3 (severe): Symptoms causing inability to perform usual activities

Grade 4 (potentially life-threatening): Symptoms causing inability to perform basic self-care functions, or if medical intervention is needed to prevent permanent impairment or death

APPENDIX C: Clinical adverse events to be monitored : Symptoms*

Systemic (General)	Mild (Grade 1)	Moderate (Grade 2)	Severe (Grade 3)	Potentially Life Threatening (Grade 4)
1. Altered feeding/Anorexia	Mild	Moderate—decreased oral intake	Severe—little oral intake	Unable to ingest food or fluid for more than 24 hours
2. Vomiting	1 episode/24 hours	2-3 episodes/24 hours	4-6 episodes/24 hours	> 6 episodes/24 hours or hypotensive shock
2. Diarrhea	3 liquid stools per 24 hours	4 liquid stools per 24 hours	Liquid stools, 5-8 per 24 hours	Liquid stools, > 8 per 24 hours, or requires hospitalization
4. Irritability	Slightly irritable, no interference with activity	Moderately irritable, some interference with activity	Significant; prevents daily activity or seeks medical attention	Incapacitating or requires hospitalization
5. Rash	Localized macular rash	Diffuse macular, maculopapular, or morbilliform rash	Grade 2 rash with vesicles, bullae, ulcerations, target lesions, or angioedema	Severe generalized rashes (e.g. Stevens Johnson syndrome, toxic epidermal necrolysis)
6. Pruritis	Localized itching, relieved spontaneously or in > 48 hours	Localized itching lasting 48 hours or longer	Generalized itching	Generalized, severe itching or generalized itching lasting > 48 hours
7. Bronchospasm or wheezing	Mild wheezing, or minimal increase in respiratory rate	Wheezing with nasal flaring, intercostal retractions, or pulse oximetry 90-95%	Wheezing with dyspnea at rest, inability to perform normal activities, or pulse oximetry <90%	Respiratory failure or anaphylaxis

* Based on NIAID Division of AIDS Table for Grading the Severity of Adult and Pediatric Adverse Events, December 2004
<http://www.niaid.nih.gov/labsandresources/resources/daidsclinrsrch/documents/daidsaegradingtable.pdf>

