34 **Specific AEs that will be monitored in this project:**

35
36 During probiotic therapy, study field workers will monitor for other potential adverse effects
37 during their home visits, based on parental interview and information recorded on a study
38 log. **Expected AEs** that are common in this study population will include fever,
39 nausea/upset stomach, vomiting, diarrhea, irritability, rash, pruritis, and wheezing or
40 bronchospasm. Diarrhea episodes will be characterized as watery or dysenteric. Space
41 will also be provided for the open end documentation of any other symptom which could

1 potentially be related to probiotic use. Appendix B and D details expected AEs and how
2 they will be graded by severity. Grading of AEs will be confirmed by the project
3 physician. AEs not listed as Expected AEs in the Toxicity Table will be reported but not
4 graded for severity. Responses to AEs encountered will be at the discretion of the project
5 physician and study monitor, based on type of AE encountered and its severity.

6 **Severity of Event:** Expected AEs will be assessed by the clinician using a protocol
7 defined grading system. For events not included in the protocol defined grading
8 system, the following guidelines will be used to quantify intensity.

9
10 Level 1 = Mild (awareness of a symptom but the symptom is easily tolerated)

11
12 Level 2 = Moderate (discomfort enough to cause interference with usual activity)

13
14 Level 3 = Severe (incapacitating; unable to perform usual activities; requires change in
15 intensity of caregiver activity or bed rest)

16
17 Level 4 = Life threatening

18
19 Changes in the severity of an AE will be documented to allow an assessment of the
20 duration of the event at each level of intensity to be performed. Adverse events
21 characterized as intermittent require documentation of onset and duration of each
22 episode.

23
24 **Method, Frequency, and Time Period for Detecting AEs**

25 At each visit, after the parent of the subject has had an opportunity to spontaneously
26 mention any problems, the investigator will inquire about AEs by asking the following
27 standard questions of the parent:

28 "Has your child had any (other) medical problems since your last visit/assessment?"

29 "Has your child taken any new medicines, other than those given to you in this study,
30 since your last visit/assessment?"

31

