11.1 Study Hypotheses and Analysis

A. The primary hypotheses are that *L. reuteri* therapy at the specified dose is safe and well-tolerated in children aged 2-24 months. There are three areas of safety and tolerability that will be assessed in this Phase 1 trial.

- 1. Evidence of bacteremia or invasive infection resulting from the administration of *L. reuteri* 17938.** Baseline and daily temperature measurements will be made during the study period during the product administration phase and then on all scheduled home visits. Complete blood counts with differential counts will be obtained at baseline, on day 5, and on day 28. The evaluation of all documented febrile episodes will include an examination by a physician, and thick smear for malaria, and blood culture for the evaluation of bacteremia if the temperature is greater than 39°C using temporal artery probe measures.

Specific outcome parameters in this category include:

- a. Mean daily temperature
- b. Incidence of fever on study days 1-5
- c. Frequency of temperature readings categorized as fever (adjusted for number of subjects per group)
- d. Number of episodes of *L. reuteri* bacteremia

2. Evidence of toxicity resulting from the *L. reuteri* DSM 17938 preparation.
Participants will have baseline, day 5, and day 28 assessment of hematologic status and

1 renal and hepatic function. Assessment of renal function will include blood urea nitrogen
2 (BUN) and creatinine (Cr). Assessment of hepatotoxicity will include transaminases
3 (AST, ALT) and total bilirubin. Hematologic status will be determined by CBC to
4 measure hemoglobin count and absolute neutrophil count, as mentioned above.

5
6 Specific outcome parameters in this category include:

7
8 a. Mean values for laboratory tests monitored (adjusted for number of subjects per
9 group). These are listed in Appendix D.
10 b. Frequency of out of range values for laboratory tests monitored (adjusted for number
11 of subjects per group). These are listed in Appendix D.

12
13 2. **Clinical tolerance.** The inclusion of a placebo group will allow for comparisons of the
14 prevalence of daily symptom measurements between treatment groups. The
15 symptoms monitored on the daily diary card (fever, anorexia/decreased oral intake,
16 vomiting, diarrhea, irritability, rash, itching, wheezing) are graded by the parent(s) of
17 the participant as mild, moderate, severe, or very severe. Parents report of severity

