18 will be analyzed, except in the case that the physician or study team deems them to be
19 more severe than reported (the study team may upgrade, but NOT downgrade the
20 severity of the symptom).

21
22 Specific outcome parameters in this category include:

23
24 a. Frequency and severity of symptoms monitored as AEs (adjusted for number of
25 subjects per group)
26 b. Frequency of all AEs (adjusted for number of subjects per group)
27 c. Frequency of SAEs (adjusted for number of subjects per group)

28
29 All continuous variables will be summarized using descriptive statistics including number
30 (N), mean, standard deviation (SD), median, maximum, and minimum. All categorical
31 variables will be summarized using frequency counts and percentages.

32
33 Changes from baseline temperature and fever graded by defined toxicity categories will
34 be summarized using descriptive statistics by treatment group.

35
36 Concomitant medications, including those taken prior to study drug administration, will be
37 listed by subject. All concomitant medications taken after initiation of the study treatment
38 will be tabulated overall and by formulation. The number and percentage of subjects who
39 take at least 1 concomitant medication and the number and percent of subjects who take
40 each specific concomitant medication will be presented.

41
42 Treatment-emergent AEs will be defined as any event with a start date occurring on or
43 after treatment Day 1 or, if pre-existing, worsening after treatment Day 1. If a subject
44 reports the same AE more than once, then that subject will only be counted once for the

1 summary of that AE, using the most severe intensity.

2
3 Treatment-emergent AEs will be summarized as follows to the DSMB during closed
4 sessions:

5 • All treatment-emergent AEs;
6 • All treatment-emergent AEs by intensity;
7 • SAEs;
8 • All treatment-emergent SAEs by relationship to study drug; and
9 • AEs that led to premature discontinuation of study drug.

10 All SAEs and AEs leading to premature withdrawal from the study will be listed.

11
12 Hematology and blood chemistry parameters will be summarized at baseline and at the
13 end of the study. Laboratory values and changes from baseline in laboratory values will
14 be summarized descriptively for all subjects and by treatment group. A summary of shifts
15 from baseline to final evaluation will be given for each parameter for all subjects and by

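### Appendix C's Grade 1 and Grade 2 pruritus cells conflict: localized itching over 48 hours fits both, and some itching under 48 hours fits neither

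*Combined protocol and SAP*

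**What the plan says.** The pruritus row of Appendix C separates localized itching (Grades 1 and 2) from generalized itching (Grades 3 and 4).

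- Grade 1: "Localized itching, relieved spontaneously or in > 48 hours".
- Grade 2: "Localized itching lasting 48 hours or longer".
- Grade 3: generalized itching, with no duration given.
- Grade 4: "Generalized, severe itching or generalized itching lasting > 48 hours".

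Appendix B gives a general scale based on interference with activity. Its Grade 1 is "Symptoms causing no or minimal interference with usual activities", and it contains no duration rule.

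Section 9.2.1 lists pruritus among the expected events and says how these are graded: "Expected AEs will be assessed by the clinician using a protocol"-defined system, with the project physician confirming the grade. Under Section 7.4, field workers check the diary card and document the severity of each event.

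Section 11.1 says that diary symptoms, itching included, are graded by the parents on a four-step scale from mild to very severe: "vomiting, diarrhea, irritability, rash, itching, wheezing) are graded by the parent(s) of" the child. The parent's grade is analysed unless the study team judges the symptom more severe. The team may raise a grade but not lower it.

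Sections 3.2.1 and 11.1 make symptom severity part of a primary tolerability parameter: "Frequency and severity of symptoms monitored as AEs (adjusted for number of" subjects per group). Section 11.1 also sends treatment-emergent events to the DSMB by intensity.

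**The concern.** A grading table should give each episode one grade. Here two adjacent cells share a 48-hour threshold but point the same way: Grade 1 admits itching that takes more than 48 hours to settle, and Grade 2 starts at 48 hours. Two members of staff could grade the same 72-hour episode differently, and both would be following the protocol.

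The Grade 1 sign also looks out of place within its own row. Grade 4 adds a duration above 48 hours to the generalized itching of Grade 3, and Grade 2 likewise covers the longer localized episodes. Only Grade 1 attaches a long duration to the milder grade.

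What is at stake is the consistency of the severity data for this symptom. Staff apply the threshold to live events, and the result feeds a primary tolerability parameter.

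**Working it through.** The plan states no figure to reproduce. The check is to write the two cells as conditions and see which grades each kind of episode meets.

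Inputs, both from Appendix C, with *d* the duration in hours of a localized episode:

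- Grade 1 is met if relief is spontaneous, **or** *d* > 48.
- Grade 2 is met if *d* ≥ 48.

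**As printed**

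| Duration | Spontaneous relief | No spontaneous relief |
|---|---|---|
| 6, 24, 47 h | Grade 1 | no grade |
| 48 h | Grades 1 and 2 | Grade 2 |
| 49, 72, 120 h | Grades 1 and 2 | Grades 1 and 2 |

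So there is an overlap (every localized episode over 48 hours, and one of exactly 48 hours if relief is spontaneous) and a gap (under 48 hours without spontaneous relief, for example after treatment). Only two situations get a single grade: under 48 hours with spontaneous relief, and exactly 48 hours without it. The overlap above 48 hours does not depend on how spontaneous relief is understood, because the second limb of Grade 1 is enough to produce it.

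**With the Grade 1 sign reversed (*d* < 48), as a test only**

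| Duration | Spontaneous relief | No spontaneous relief |
|---|---|---|
| 6, 24, 47 h | Grade 1 | Grade 1 |
| 48 h | Grades 1 and 2 | Grade 2 |
| 49, 72, 120 h | Grades 1 and 2 | Grade 2 |

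The gap closes and the right-hand column is clean. The left-hand column still overlaps from 48 hours on, because the spontaneous-relief limb has no time limit.

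**Does another provision settle the grade?**

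- Grades 3 and 4 cover generalized itching only.
- Appendix B uses a different criterion, interference with activity, and is not a tie-break on duration.
- The four-level fallback scale in Section 9.2.1 is for events outside the protocol's grading system; pruritus is inside it.
- The rule in Section 11.1 that a subject is counted once in the "summary of that AE, using the most severe intensity" applies when the same event is reported more than once. It does not choose between two grades for one episode.
- The confirming physician works from the same table.

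**Size in the tables.** Sixty children randomized 2:1 gives 60 × 2/3 = 40 active and 60 × 1/3 = 20 placebo. One child moved between mild and moderate changes that arm's percentage by 1/40 = 2.5 points or 1/20 = 5 points. The documents give no expected frequency of prolonged localized itching, so the number of children affected cannot be estimated.

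**The case against.** The strongest reply is that little depends on this boundary.

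- The analysed diary severity is the parent's own grade. Appendix C then matters mainly when staff decide whether to raise a mild report, and a physician confirms grading. This stands as a limit on the effect. It does not remove the problem, since both the decision to raise a grade and the confirmation rest on the conflicting cells.
- No trial action turns on it. Grade-triggered SAE status applies to laboratory values (Sections 9.2.2 and 9.2.4), halting to similar SAEs (Sections 9.5 and 11.3.1), the fever work-up to fever grade, and exclusion criterion 6 to the presence of a monitored event, not its grade. This stands in full.
- The sign could be a text-extraction error. That cannot be ruled out, but other inequality signs in the same table, such as those for pulse oximetry and for vomiting and stool counts, read sensibly. Even with the opposite sign, the spontaneous-relief overlap remains.

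A reader might also infer more than the documents support. One inference is that the severity of localized itching is undefined altogether; it is not, because short, spontaneously relieved itching is plainly Grade 1. Another is that the comparison between arms is biased; graders are masked under Section 5.4.2, so the expected harm is inconsistency, not a systematic shift. A third is that a one-character correction would be enough; the second table shows otherwise.

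**Conclusion.** The two cells contradict each other as printed, and no other provision resolves the conflict. It is a minor wording defect, worth correcting because staff use the table to grade events that enter a primary tolerability parameter and the DSMB summary by intensity. Its reach is the mild/moderate boundary of one of seven symptoms. Counts of events, SAE classification, halting and eligibility are unaffected, as are Grades 3 and 4.

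The conclusion assumes that the inequality is printed in the protocol as it reads here, and that the two limbs of Grade 1 are alternatives, either of which is sufficient.

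**What to change.** Reconcile and reword the Grade 1 and Grade 2 pruritus cells together. The new wording should settle three things: the direction of the inequality, whether spontaneous relief carries a time limit, and where a short episode relieved by treatment belongs. Each localized episode, including one of exactly 48 hours, should then map to one grade. The choice of cut-off is a clinical matter for the sponsor.

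Use the same wording on any form or instruction that staff use for grading. If any children have been graded before the change, list their localized itching episodes and regrade them under the new wording while the team is still masked.

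The cost is one or two reworded table cells and matching text on the grading forms. No visit, sample or analysis changes.

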APPENDIX D: LABORATORY VALUES*

Serum Chemistries (normal range for 0-2 year old children at our reference lab)	Mild (Grade 1)	Moderate (Grade 2)	Severe (Grade 3)	Potentially Life Threatening (Grade 4)**
8. Bilirubin, mg/dL (\leq 1.0)	1.1-1.9	2.0-2.9	3.0-7.5	>7.5
9. Blood Urea Nitrogen BUN mg/dL (\leq 23)	24-60	61-80	\geq 81	Requires dialysis
10. Creatinine, mg/dL (\leq 0.4)	0.5 – 1.0	1.1 – 1.6	1.7 – 2.0	> 2.0 or requires dialysis
11. Liver Function Tests –ALT (\leq 52) units per liter (U/L)	53-200	201-400	401-600	> 600
12. Liver Function Tests –AST (\leq 39) units per liter (U/L)	40-200	201-400	401-600	> 600

Hematology	Mild (Grade 1)	Moderate (Grade 2)	Severe (Grade 3)	Potentially Life Threatening (Grade 4)
13. Children 6-24m : Hemoglobin gm/dL (\geq 11)	10.0 – 10.9	7.0 – 9.9	< 7.0	Cardiac insufficiency due to anemia
13a. Children 2-5 m: Hemoglobin gm/dL (\geq 9.5)	9.4-8.5	6.5-8.4	<6.5	Cardiac insufficiency due to anemia
14. Total WBC Count - cell/mm ³ (6,000-17,500)	17,501 – 20,000	20,001 – 25,000	25,001 – 28, 000	> 28,000

* Based on NIAID Division of AIDS Table for Grading the Severity of Adult and Pediatric Adverse Events, December 2004
(<http://www.niaid.nih.gov/labsandresources/resources/daidsclinrsrch/documents/daidsaegradingtable.pdf>), adapted for normal reference values for age for our reference laboratory (Asociacion Civil Selva Amazonica: Iquitos, Peru; www.selvaamazonica.org)

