32 **Relationship to Study Products:** AEs will be assessed for relationship to study product.
33 The clinician's assessment of an AE's relationship to test article (study drug) is part of
34 the documentation process, but it is not a factor in determining what is or is not reported
35 in the study. If there is any doubt as to whether a clinical observation is an AE, the event
36 will be reported. All AEs must have their relationship to study product assessed using
37 the terms: associated or not associated.

38
39 In a clinical trial, the study product must always be suspect. To help assess, the
40 following guidelines will be used.

41 • **Associated** – The event is temporally related to the administration of the study

1 product and no other etiology explains the event.

2 • **Not Associated** – The event is temporally independent of study product and/or the
3 event appears to be explained by another etiology.

4

5

6 9.2.2 Serious Adverse Events (SAE)

7

8 **Definition of a Serious Adverse Experience (SAE):**

9 Serious adverse event (SAE): A Serious Adverse Event is defined as an AE meeting one
10 of the following conditions

11

12 • Death during the 3 month period of protocol defined surveillance

13

14 • Life Threatening Event (defined as a subject at immediate risk of death at the time
15 of the event)

16

17 • An event requiring inpatient hospitalization or prolongation of existing
18 hospitalization during the period of protocol defined surveillance

19

20 • Results in persistent or significant disability/incapacity

21

22 • Any episode of bacteremia due to *Lactobacillus reuteri*, the study probiotic

23

24 • Any other important medical event that may not result in death, be life threatening,
25 or require hospitalization, may be considered a serious adverse experience when,
26 based upon appropriate medical judgment, the event may jeopardize the subject
27 and may require medical or surgical intervention to prevent one of the outcomes
28 listed above. Examples of such medical events include allergic bronchospasm
29 requiring intensive treatment in an emergency room or convulsions that do not
30 result in inpatient hospitalization.

31

32 • Any monitored lab value meeting the Grade 3 or Grade 4 toxicity criteria

33

34 **Bacteremia:** Any episode of bacteremia due to *Lactobacillus reuteri*, the study probiotic,
35 will be considered a Serious Adverse Event. Subjects started on probiotic/placebo

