- provision of additional information about newly recognized risks to previously enrolled subjects.

Some incidents, experiences, and outcomes that occur during the conduct of human subjects research represent unanticipated problems but are not considered adverse events. These may involve social or economic harm instead of the physical or psychological harm associated with adverse events. In other cases, unanticipated problems place subjects or others at increased risk of harm, but no harm occurs. Unanticipated problems must be reported, even if they do not involve adverse events. However, adverse events that do not meet the criteria to be considered unanticipated problems are not subject to these reporting requirements.

Incidents or events that meet the OHRP criteria for unanticipated problems involving risks to subjects or others require the completion of an AE report form.

Additional reporting requirements. Abuse or illegal activities will be reported to Peruvian authorities in a manner consistent with local laws. A written note, documenting the concern, and witnessed of reported behavior giving rise to the concern, is issued to the Peruvian community designated “Defensor de Pueblo” the local legal authority that investigates cases of child abuse and exploitation.

9.2.4 Procedures to be Followed in the Event of Abnormal Laboratory Test Values or Abnormal Clinical Findings

Baseline lab tests will be reviewed by the study physician as part of the screening process. In order to be eligible to participate in the study, all monitored baseline laboratory values must be within the normal range for the reference laboratory.

1 Laboratory values provided by the clinical laboratory that are not among the group of
2 monitored laboratory tests do not have to be within the normal range in order for a
3 consented subject to become a participant, but these reportedly abnormal values will
4 be noted on the FORM FOR EVALUTION OF LABORATORY VALUES. These non-
5 monitored laboratory values provided as part of the complete blood count (CBC)
6 include platelet count and percentage of various leukocyte categories in the differential.
7 Monitored laboratory values are:

8

- 9 • Hemoglobin
- 10 • Total leukocyte count
- 11 • Total serum bilirubin
- 12 • Blood urea nitrogen (BUN)
- 13 • Creatinine
- 14 • Alanine transaminase (ALT)
- 15 • Aspartate aminotransferase (AST)

16

17 Monitored laboratory values will be reviewed by the study physician within 48 hours of

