18 receiving the report from the reference laboratory, and values will be recorded on the
19 appropriate CRF (FORM FOR EVALUATION OF LABORATORY VALUES). Abnormal
20 values meeting toxicity level 1 or 2 which do not warrant further clinical investigation will
21 be noted as such on the laboratory values CRF along with an assessment of
22 relationship to the study product. These abnormal values will be reported to the
23 oversight agencies as AEs according to procedures described below. Abnormal
24 values meeting toxicity level 1 or 2 which may, in the judgment of the study physician,
25 warrant further investigation will result in a clinic visit for full evaluation recorded on the
26 ADVERSE EVENT CRF and will be followed to completion and resolution as with other
27 AEs. Abnormal values meeting toxicity levels 3 or 4 will be considered SAEs and will
28 be evaluated, monitored, and reported according to procedures described for SAEs.

29

30 **Documenting AEs**

31 Any AE occurring during the study must be documented in the subject's medical records
32 and on the appropriate AE CRF, i.e. the AE Report Form. Information to be collected on
33 the AE Report Form includes event description, time of onset, investigator assessment of
34 severity, and relationship to the study product, time of resolution of the event, seriousness,
35 and outcome. All adverse events occurring during the study must be documented
36 appropriately regardless to the relationship of the event with study participation.

37

38 The investigator or study physician should attempt to establish a diagnosis of the event
39 based on signs, symptoms, and/or other clinical information. A diagnosis, if known, or
40 clinical signs and symptoms if diagnosis is unknown, rather than the clinically significant
41 abnormal laboratory finding, should be completed on AE CRF form. If no diagnosis is
42 known and clinical signs and symptoms are not present, then the abnormal finding should
43 be recorded. The laboratory data should either be recorded on the AE forms with the
44 reference range and baseline value(s) or copies of the laboratory reports and reference
45 ranges should be sent with the CRF pages.

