9.3.1 Serious Adverse Events

Any AE considered serious by the study physician or which meets the aforementioned criteria must be submitted on a SAE form to the appropriate IRBs, INS, DSMB designate and the NIDDK. The SAE form will be sent as an email attachment or fax to each relevant institutional representative within the time frame below:

* All deaths, whether related or unrelated, will be recorded on the Serious Event Form and on MedWATCH FDA 3500 (2/13) and sent by fax and email within 24 hours of the site awareness of the death.

* Serious adverse events other than death, regardless of relationship, will be reported via fax and email by the site within 24 hours of becoming aware of the event.

Other supporting documentation of the event may be provided upon request as soon as possible.

All serious adverse events will be:

- recorded on the appropriate serious event case report form
- followed through resolution by a study physician
- reviewed by a study physician

All SAEs will be followed until satisfactory resolution of the event or until the study physician deems the event to be chronic or the patient to be stable.

1 The investigator, or responsible person according to local requirements, must comply with
2 the applicable local regulatory requirements related to the reporting of SAEs to regulatory
3 authorities and the IRB/EC.

4
5 **SAEs will be reported to the institutional representatives at the fax and email**
6 **addresses shown in the section entitled Reporting of Adverse Events.**

7
8
9
10 **9.3.2 Regulatory Reporting for Studies Not Conducted Under**
11 **NIDDK-Sponsored IND**

12
13 Procedures for reporting AEs and SAEs are described in the corresponding sections on
14 AE and SAE reporting.

15
16
17 **9.4 Type and Duration of Follow-up of Subjects after Adverse**
18 **Events**

19
20 **Follow-up of AEs**
21 All AEs will be followed until resolution, until the condition stabilizes, until the event is
22 otherwise explained, or the subject is lost to follow-up. The ADVERSE EVENT CRF
23 includes space for up to two follow-up visits for the same AE. The investigators will
24 ensure that follow-up includes any supplemental investigations as may be indicated to
25 elucidate as completely as practical the nature and/or causality of the AE. This may
26 include additional laboratory tests or investigations, histopathological examinations, or
27 consultation with other health care professionals. New or updated information should be

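### Appendix D grades white cell count only above its two-sided normal range, so the automatic Grade 3-4 SAE rule cannot fire on a low count

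*Combined protocol and SAP*

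**What the plan says.** Appendix D lists eight laboratory rows, each with a normal limit or range and four grades. The row "14. Total WBC Count - cell/mm" has a normal range of 6,000-17,500 and these grades: 17,501-20,000, 20,001-25,000, 25,001-28,000 and above 28,000. The two rows "13. Children 6-24m : Hemoglobin gm/dL" and "13a. Children 2-5 m: Hemoglobin gm/dL" have only a lower normal limit and are graded downward from it. The five chemistry rows have only an upper limit and are graded upward.

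Section 9.2.4 lists "Total leukocyte count" among the monitored values and ties its actions to toxicity level. Abnormal "values meeting toxicity level 1 or 2 which do not warrant further clinical investigation will" be noted on the laboratory form and reported as AEs. For the higher levels, "Abnormal values meeting toxicity levels 3 or 4 will be considered SAEs and will" follow the SAE procedures. Section 9.2.2 includes in its SAE definition "Any monitored lab value meeting the Grade 3 or Grade 4 toxicity criteria".

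SAE status has consequences. Section 9.3.1 states: "Serious adverse events other than death, regardless of relationship, will be reported via fax and email by the site within 24 hours". Sections 9.5 and 11.3.1 halt the study when two or more children have similar SAEs whose relationship to product cannot be excluded.

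**The concern.** The protocol chose number-based rules for its monitored laboratory tests, and for one direction of one test the number is missing. Sections 3.2.1 and 11.1 collect the blood count as evidence on both invasive infection and toxicity. Section 9.2.4 requires monitored baseline values to be normal, and exclusion criterion 9 in Section 5.2 removes children with an out-of-range leucocyte count. A child at 5,900 could not be enrolled, so a low count on day 5 or 28 is a new change after dosing. Yet an enrolled child who falls to 500 reaches no Appendix D grade.

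What is at stake is uniform escalation. Two children with the same low count could be classed differently by different physicians, and nothing in the table settles it. The summary of treatment-emergent AEs by intensity (Section 11.1) would also have no Appendix D grade to use for such an event.

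**Working it through.** The plan states no figure to reproduce here. The check is a reading of Appendix D row by row, followed by tracing the rules that depend on a grade.

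**Step 1: is every abnormal side graded?** Values are as printed in Appendix D.

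| Row | Normal | Grade 1 begins | Ungraded abnormal side |
|---|---|---|---|
| 8 Bilirubin, mg/dL | ≤ 1.0 | 1.1, upward | none |
| 9 BUN, mg/dL | ≤ 23 | 24, upward | none |
| 10 Creatinine, mg/dL | ≤ 0.4 | 0.5, upward | none |
| 11 ALT, U/L | ≤ 52 | 53, upward | none |
| 12 AST, U/L | ≤ 39 | 40, upward | none |
| 13 Hemoglobin 6-24 m, g/dL | ≥ 11 | 10.9, downward | none |
| 13a Hemoglobin 2-5 m, g/dL | ≥ 9.5 | 9.4, downward | none |
| 14 White cells, per mm³ | 6,000-17,500 | 17,501, upward | below 6,000 |

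Seven of the eight rows grade every value outside their printed normal range. For white cells, 4 of 4 grades lie above 17,500 and 0 of 4 lie below 6,000. Applying the row to each whole-number count gives a grade to 0 of the 6,000 values from 0 to 5,999, and to all 22,500 values from 17,501 to 40,000.

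**Step 2: could a row have been lost in the text?** The items run 13, 13a, 14, and then 15 in Appendix E, so no numbered white cell row appears to be missing. The double asterisk on the chemistry Grade 4 heading has no footnote in the text, but that mark is not on the hematology heading.

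**Step 3: trace example values through Sections 9.2.2 and 9.2.4.**

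| Count | Distance from limit | Appendix D grade | SAE by rule? |
|---|---|---|---|
| 17,501 | just above 17,500 | 1 | no |
| 25,001 | 25,001/17,500 = 1.43, 43% above | 3 | yes |
| 28,001 | 28,001/17,500 = 1.60, 60% above | 4 | yes |
| 5,999 | just below 6,000 | none | no |
| 3,000 | 1 − 3,000/6,000 = 50% below | none | no |
| 500 | 1 − 500/6,000 = 92% below | none | no |

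The percentages only locate the values. A given percentage above the range is not clinically equivalent to the same percentage below it.

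**Step 4: how many results does the one-sided row govern?** 60 children × 2 scheduled post-baseline draws (days 5 and 28) = at most 120 results. This counts draws, not affected children.

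**Step 5: does another scale supply the grade?** Section 9.2.1 gives a generic Level 1-4 scale for events outside the protocol's grading system. The same section also says that AEs not listed in the toxicity table are reported without a severity grade, and Section 7.4 says this again for AEs outside Appendices C, D and E. The text therefore conflicts on whether the generic scale applies. If it does apply, it is worded in terms of symptoms, usual activity and threat to life, so it does not turn a count in a well child into a level. Either way no numeric trigger results.

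**The case against.** The strongest objection is that little is lost, and much of it stands.

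- **AE capture is intact.** A reader might infer that a low count goes unrecorded or cannot be an AE. The documents do not support that. Section 9.2.1 counts an abnormal laboratory finding as an AE, requires AEs within 90 days to be documented whatever their cause, and resolves doubt in favour of reporting.
- **SAE status remains possible.** A reader might also infer that a profound leukopenia could never be an SAE. It could, through the important-medical-event criterion in 9.2.2 or the physician's own classification under 9.3.1. Only the automatic route is absent.
- **The value is seen.** A physician reviews monitored results within 48 hours (9.2.4), out-of-range frequency is an outcome (3.2.1), the shift tables have a low category (11.1), and the DSMB sees out-of-range values by arm (9.6). However, 9.2.4 sets actions only by toxicity level, so the review has no defined action for a low count, and the DSMB report is quarterly. If accrual were even over the planned four months and the first review fell at month three, 60 × 3/4 = 45 children would already be randomised.
- **Serious infection has its own triggers.** Fever of Grade 3 or 4 or a toxic appearance leads to physician evaluation and blood culture, and *L. reuteri* bacteremia and hospitalization are SAEs by definition (7.4, 9.2.2). It would be wrong to say that sepsis would be missed.
- **High counts also involve judgment.** Whether a Level 1-2 value needs further investigation is the physician's call, and the halt requires review of relationship (9.5). No number halts the trial alone.
- **Stopping product is nearly moot.** The day-5 blood is drawn with the final dose (7.4), so at most a make-up dose (6.5) could remain.

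These points reduce the consequence. They do not supply the missing grade.

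**Conclusion.** The point holds in a narrow form. A low white cell count has no Appendix D grade, so the Grade 3-4 SAE rule cannot fire on it. The 24-hour report and eligibility to count toward the two-similar-SAE halt then depend on a physician judging the event serious. This is a defect in a stated safety rule and worth correcting before enrolment.

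Its size is one direction of one monitored test, one of eight rows, and at most 120 scheduled results. A reader might infer bias in the comparison of arms, but the documents do not support that: the row is the same for both groups, and low values enter the laboratory outcomes. The documents describe no white-cell-lowering signal for this product, so no event rate is claimed.

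The conclusion assumes that Appendix D is complete as printed. The text between the end of 9.2.4 and 9.3.1 was not available, so nothing is claimed about reporting routes described there.

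**What to change.** Before enrolment, add a low-side white cell row to Appendix D. Start Grade 1 just below 6,000, as the other rows start at their normal limits, and make Grades 2-4 contiguous below it. The protocol gives no low cut-offs, and none are proposed here. The sponsor should set them from the grading table and reference-laboratory ranges that the appendix already cites. Grades 3 and 4 should sit far enough below 6,000 that minor dips do not become SAEs or feed the halting rule.

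The change needs no extra blood, assay or visit. The cost is a few more graded laboratory AEs to process, mostly small dips at Grade 1 if the cut-offs are well placed.
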